### **7.4. Other Safety Analyses**

The analyses of non-laboratory safety test results include vital signs, ECGs, pregnancy test and Columbia Suicide-Severity Rating Scale (C-SSRS).

#### **7.4.1. Vital Signs**

Each vital sign parameter at every assessed time point will be summarized. The change from baseline for each vital sign parameter will also be summarized.

A listing of all vital sign values for subjects who had any value of potential clinical importance during the study will be provided. A listing of vital sign values of potential clinical importance only will also be provided.

The summary will be displayed overall for Screening, Day 0 and Day 11, and by treatment group A/B (A: Paroxetine IR 40 mg GSKT tablet; B: Paroxetine IR 40 mg Mississauga tablet) for other time points.

#### **7.4.2. 12-Lead Electrocardiogram**

Each ECG parameter at every assessed time point will be summarized. A summary of mean change from baseline in ECG values will also be provided. A by-subject listing of all ECG values for subjects who had any value of potential clinical importance during the study will be provided. A listing of ECG values of potential clinical importance only will also be provided.

A summary of the number and percentage of subjects who had abnormal with/without clinically significant ECG findings will be displayed. A by-subject listing of all ECG data for subjects with an abnormal finding during the study will be provided. A by-subject listing of abnormal ECG findings only will also be provided.

The summary will be displayed overall for Screening and by treatment group A/B for post-baseline time points (A: Paroxetine IR 40 mg GSKT tablet; B: Paroxetine IR 40 mg Mississauga tablet).

#### **7.4.3. Pregnancy**

The pregnancy information will be summarized and a listing of all pregnancies will be provided.

#### **7.4.4. Columbia Suicide-Severity Rating Scale (C-SSRS)**

The C-SSRS information and possible suicidality-related adverse event will be listed.

## 8. PHARMACOKINETIC ANALYSES

All the pharmacokinetic analyses will be based on the “Pharmacokinetic” population, and displayed separately for each group (Fasting or Fed).

All the PK summary will be displayed by treatment group A/B (A: Two Paroxetine IR 40mg GSKT tablets; B: Two Paroxetine IR 40mg Mississauga tablets).

Pharmacokinetic analyses will be based on GSK data standards and statistical principles. Details of the planned pharmacokinetic displays will be provided in [Appendix 7: List of Data Displays of Full RAP](#).

### 8.1. Endpoint / Variables

#### 8.1.1. Drug Concentration Measures

Concentrations of Paroxetine in plasma will be summarized and listed. Standard summary statistics will be calculated (i.e. mean, standard deviation, median, minimum and maximum).

Individual plasma concentration-time profiles and median/mean profiles will be plotted. Each of the figures will contain one plot on the untransformed scale (i.e. a linear plot) and one plot on the log transformed scale (i.e. log-linear plot). Mean profiles will be plotted with standard deviation bar. Median profiles will be plotted with range bar.

Refer to [Appendix 2: Data Display Standards & Handling Conventions \(Section 10.2.3 Reporting Standards for Pharmacokinetic\)](#) for details.

#### 8.1.2. Derived Pharmacokinetic Parameters

Pharmacokinetic parameters will be calculated by standard non-compartmental analysis according to current working practices and using the currently supported version of WinNonlin 6.3 or higher version. All calculations of non-compartmental parameters will be based on actual sampling times. Pharmacokinetic parameters listed will be determined from the plasma concentration-time data for Paroxetine, as data permits.

Parameter	Parameter Description
$AUC_{0-\infty}$	Area under the concentration-time curve from time zero extrapolated to infinite time
$AUC_{(0-t)}$	Area under the concentration-time curve from administration extrapolated to the last time of quantifiable concentration, calculated as logarithm of trapezoid area.
$C_{max}$	The observed maximum drug concentration
$T_{max}$	Time to reach $C_{max}$
$t_{1/2}$	Terminal elimination half-time
$\lambda_z$	Terminal elimination rate constant
CL/F	Oral clearance
Vd/F	Apparent volume of distribution
MRT	Mean residence time

For each of the derived parameters described above, except  $T_{max}$ , the following summary statistics will be calculated: arithmetic mean, 95% confidence interval for the arithmetic mean, standard deviation, median, minimum, maximum of untransformed data, geometric mean, 95% confidence interval for the geometric mean, standard deviation and coefficient of variation of logarithmically transformed data. For  $T_{max}$ , arithmetic mean, 95% confidence interval for the arithmetic mean, standard deviation, median, minimum and maximum will be calculated.

## 8.2. Statistical Analyses / Methods

After  $\log_e$ -transformation,  $AUC_{(0-\infty)}$ ,  $AUC_{(0-t)}$  and  $C_{max}$  will be analyzed, each separately, using mixed effect model. The model will include period and treatment as fixed effects, and participant as random effects. The covariance structure of the G matrix will be specified as unstructured, and the Kenward and Roger method for approximating the denominator degrees of freedom will be used.

Point estimates and their associated adjusted 90% confidence interval within A or B will be provided for the above mentioned PK parameters in log scale. All the data will be used to calculate for the within-treatment analysis.

Point estimates and their associated adjusted 90% confidence interval of difference between A and B will be provided for the above mentioned PK parameters in log scale.

If the 90% confidence interval of  $AUC_{(0-\infty)}$ ,  $AUC_{(0-t)}$  ( $AUC_{(0-t)}$  only if  $AUC_{(0-\infty)}$  can't be accurately determined) and  $C_{max}$  fall in the range of 0.80-1.25, it can be stated that the two formulations are bioequivalent.

```
PROC MIXED data=PK;  
  
  class seq subject trt Period;  
  
  model log(PKParm)= seq trt Period/solution ddfm=satterth;  
  
  random intercept/subject=subject(seq) type=un;  
  
  lsmeans trt/cl diff alpha=0.1;  
  
run;
```

The point estimates and their associated adjusted 90% confidence intervals will then be back-transformed.

Within subject coefficient of variation (%CVw) for transformed data will be calculated according to the following methods:

$$\%CV_w = \text{SQRT}(\exp(\text{mse}) - 1) \times 100$$

where mse is the residual error from the model for log-transformed data.

Unless otherwise specified, endpoints / variables defined in Section 8.1 will be summarised using descriptive statistics and listed, and BE population will be used for analysis.

Sensitivity analysis will be performed on BE population excluding the subjects with I/E violation.

## 10. APPENDICES

### 10.1. Appendix 1: Study Phases and Adverse Events

#### 10.1.1. Treatment States for AE data

Treatment State	Definition
Onset Time Since First Dose (Days)	If Treatment Start Date > AE Onset Date, onset time since first dose= AE Onset Date - Treatment Start Date If Treatment Start Date ≤ AE Onset Date, onset time since first dose = AE Onset Date - Treatment Start Date +1 Missing otherwise
Duration (Days)	AE Resolution Date – AE Onset Date + 1
Drug-related	If relationship is marked 'YES' on eCRF or value is missing

**NOTES:**

- If AE onset is during one period and worsens during a later period it would be counted in both periods.

## 10.2. Appendix 2: Data Display Standards & Handling Conventions

### 10.2.1. Reporting Process

Software

 
The currently supported versions of SAS software will be used.
 

Analysis Datasets

 
Analysis datasets will be created according to CDISC standards (SDTM IG Version 3.2 & ADaM IG Version 1.0).
 

Generation of RTF Files

 
Both RTF and bookmarked PDF files will be generated.
 

### 10.2.2. Reporting Standards

General

 
The current GSK Integrated Data Standards Library (IDSL) will be applied for reporting, unless otherwise stated (IDSL Standards Location: https://spope.gsk.com/sites/IDSLLibrary/SitePages/Home.aspx):             
 
4.03 to 4.23: General Principles
 
5.01 to 5.08: Principles Related to Data Listings
 
6.01 to 6.11: Principles Related to Summary Tables
 
7.01 to 7.13: Principles Related to Graphics
 
 
 

Formats

 
All data will be reported according to the actual treatment the subject received unless otherwise stated.
 
GSK IDSL Statistical Principles (5.03 & 6.06.3) for decimal places (DP's) will be adopted for reporting of data based on the raw data collected, unless otherwise stated.
 
Numeric data will be reported at the precision collected on the eCRF.
 
The reported precision from non eCRF sources will follow the IDSL statistical principles but may be adjusted to a clinically interpretable number of DP's.
 

Planned and Actual Time

 
Reporting for tables, figures and formal statistical analyses:             
 
Planned time relative to dosing will be used in figures, summaries, statistical analyses and calculation of any derived parameters, unless otherwise stated.
 
The impact of any major deviation from the planned assessment times and/or scheduled visit days on the analyses and interpretation of the results will be assessed as appropriate.
 
 
 
Reporting for Data Listings:             
 
Planned and actual time relative to study drug dosing will be shown in listings (Refer to IDSL Statistical Principle 5.05.1).
 
Unscheduled or unplanned readings will be presented within the subject's listings.
 
 
 

Unscheduled Visits

 
Unscheduled visits will not be included in by-visit summary tables and figures.
 
All unscheduled visits will be included in listings.
 

Descriptive Summary Statistics	
Continuous Data	Refer to IDSL Statistical Principle 6.06.1
Categorical Data	N, n, frequency, %
Graphical Displays	

 
Refer to IDSL Statistical Principals 7.01 to 7.13.
 
	

### 10.2.3. Reporting Standards for Pharmacokinetic

Pharmacokinetic Concentration Data	
PC WinNonlin (WNL) File	PC WNL file (CSV format) for the non compartmental analysis by Clinical Pharmacology Modelling and Simulation function will be created according to current working practices. Note: Concentration values will be imputed as per GUI_51487
Descriptive Summary Statistics, Graphical Displays and Listings	Refer to IDSL PK Display Standards. Refer to IDSL Statistical Principle 6.06.1. Note: Concentration values will be imputed as per GUI_51487 for descriptive summary statistics/analysis and summarized graphical displays only.
Pharmacokinetic Parameter Derivation	
PK Parameter to be Derived by Clinical Pharmacology Modelling and Simulation team	All the PK parameters will be derived by the Clinical Pharmacology Modelling and Simulation team
Pharmacokinetic Parameter Data	
Descriptive Summary Statistics, Graphical Displays and Listings	Refer to IDSL PK Display Standards.  N, n, arithmetic mean, median, min, max, SD, 95% CI of arithmetic mean will be provided for untransformed data.  For log-transformed data, N, n, geometric mean, 95% CI of geometric mean, standard deviation (SD) and between subject coefficient of variation (CVb (%)) of log-transformed data will be reported. $CVb (\%) = \text{SQRT}(\exp(SD^2)-1) * 100$ Where SD is the standard deviation of the log e -transformed data.
Parameters Not Being Log Transformed	T max

### 10.3. Appendix 3: Derived and Transformed Data

#### 10.3.1. General

Multiple Measurements at One Analysis Time Point

 
• Mean of the measurements will be calculated and used in any derivation of summary statistics but if listed, all data will be presented.
 
• Participants having both High and Low values for Normal Ranges at any post-baseline visit for safety parameters will be counted in both the High and Low categories of “Any visit post-baseline” row of related summary tables. This will also be applicable to relevant Potential Clinical Importance summary tables.
 

Study Day

 
• Calculated as the number of days from First Dose Date:             
 
• Ref Date = Missing → Study Day = Missing
 
• Ref Date < First Dose Date → Study Day = Ref Date – First Dose Date
 
• Ref Date ≥ First Dose Date → Study Day = Ref Date – (First Dose Date) + 1
 
 
 

#### 10.3.2. Study Population

Age

GSK standard IDSL algorithms will be used for calculating age where birth date is imputed as:
 
 
• Any subject with a missing day will have this imputed as day ‘15’.
 
• Any subject with a missing date and month will have this imputed as ‘30th June’.
 
• Birth date will be presented in listings as ‘YYYY’.
 

Body Mass Index (BMI)

 
• Calculated as Weight (kg) / [Height (m)]
 

#### 10.3.3. Safety

Laboratory Parameters

 
• If a laboratory value which is expected to have a numeric value for summary purposes, has a non-detectable level reported in the database, where the numeric value is missing, but typically a character value starting with ‘<x’ or ‘>x’ (or indicated as less than x or greater than x in the comment field) is present, the number of significant digits in the observed values will be used to determine how much to add or subtract in order to impute the corresponding numeric value.
 
• Example 1: 2 Significant Digits = ‘< x’ becomes x – 0.01
 
• Example 2: 1 Significant Digit = ‘> x’ becomes x + 0.1
 
• Example 3: 0 Significant Digits = ‘< x’ becomes x – 1
 

**10.3.4. Pharmacokinetic****PK**

- Plasma sample analysis will be carried out by Bioanalytical Service at Wuxi AppTec. Paroxetine plasma concentrations will be determined using the currently validated methodology. The actual sampling times, if different from protocol, will be used in the PK calculations. Please refer to the rules in Section 10.4.1 for the plasma concentrations below Limit of quantification (LOQ).
- Paroxetine plasma concentration-time data will be analyzed by non-compartmental methods with WinNonlin 6.3 or above and derived PK parameters will be summarised and listed. Derived Pharmacokinetic parameters will be summarized by treatment group. Mean, Median, Min, Max, SD, GeoMean, log SD, CVb, 95% CI will be provided; Individual and mean, median PK concentration-time curves will be provided.

## 10.4. Appendix 4: Reporting Standards for Missing Data

### 10.4.1. Premature Withdrawals

Element	Reporting Detail
General	
 
• Subject study completion (i.e. as specified in the protocol) was defined as completion of all phases of the study including the follow-up visit.
 
• Withdrawn subjects will not be replaced in the study.
 
• All participants who withdraw prematurely from the study will be documented and the reason for their withdrawal recorded in the final Clinical Pharmacology Study Report (CPSR).
 
• All available data from participants who were withdrawn from the study will be listed and all available planned data will be included in summary tables and figures, unless otherwise specified.
 
• In the event that the study is prematurely discontinued, all available data will be listed and a review carried out by the study team to assess which statistical analyses are still considered appropriate.
 

### 10.4.2. Handling of Missing Data

Element	Reporting Detail
General	
 
• Missing data occurs when any requested data is not provided, leading to blank fields on the collection instrument: 
 
○ These data will be indicated by the use of a “blank” in subject listing displays. Unless all data for a specific visit are missing in which case the data is excluded from the table.
 
○ Answers such as “Not applicable” and “Not evaluable” are not considered to be missing data and should be displayed as such.
 
 
 

Outliers	
 
• Any participants excluded from the summaries and/or statistical analyses will be documented along with the reason for exclusion in the clinical study report.
 

PK	
 
• Concentrations which are below the LLQ (“lower limit of quantification” for the analyte in question) are listed as NQ in the raw concentration data provided by DMPK. Several derived variables exist for the imputation of these concentrations.
 
• The following variables exist in the PKCNC dataset for different imputations of the raw concentration data; 
 
PCORRES: Original result
 
PCSTRESN: Original result in standard units
 
PCSTIMPN: Imputed result for use in the calculation of summary statistics
 
PCSTIMSN: Imputed result for individual concentration plots
 
PCWNLN: Imputed result for use in WinNonlin analysis
 
 
 
• The imputation of NQs for variables in the PKCNC file will be based on that defined in GUI_51487, under the section “How to Handle Values Below the Quantification Limit”. A brief summary is provided in the table below.
 

Element	Reporting Detail					
	Variable	Leading NQ	Single NQ between measurable concentrations	More than one consecutive NQ between measurable concentrations	Measurable concentrations after more than one consecutive mid-profile NQ*	Trailing NQ (consecutive NQs in the tail)
	PCSTIMP	0	NULL	0	NULL	0
	PCSTIMSN	0	NULL	0	No Action	NULL
	PCWNLN	0	NULL	NULL	NULL	NULL

* a mid-profile NQ is defined as any NQ where measurable concentrations exist both before and after that NQ in the profile
						

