### 2.3. Study Design

Overview of Study Design and Key Features	

The diagram illustrates the study design timeline from Day -7 to Day 28. It is divided into several phases: Screening (Days -7 to -1), Randomization (Day 0), First Period (Days 1-5), Washout (Days 6-11), Second Period (Days 12-16), and Follow-up (Days 17-28). Two groups are shown: Fed Group and Fasting Group. Each group is randomized into two sequences: AB and BA. In the AB sequence, Drug A is administered on Day 1 and Drug B on Day 12. In the BA sequence, Drug B is administered on Day 1 and Drug A on Day 12. Sampling points are indicated by orange boxes between Day 1-5 and Day 12-16. A vertical dashed line at Day 0 marks the start of randomization.
	
Design Features	
 
A single dose, open-label, randomized, two-way crossover study to demonstrate the bioequivalence of Paroxetine IR tablets manufactured in GSKT (A) and Mississauga (B) sites in healthy Chinese participants under fasting and fed conditions.
 

Dosing	
 
On Day 1, each enrolled participant will take a single dose of Paroxetine IR 40mg (20mg*2 tablets) A or B.
 
Following a washout from Day 6 to Day 11, participants will be crossed over in Period 2 to receive the treatment that they did not receive in Period 1. Eligible participants will take Paroxetine IR 40mg (20mg*2 tablets) A or B once on Day 12.
 

Treatment Assignment	
 
The whole study will be divided into two groups, one for fasting condition and another for fed condition. For each group, eligible participants will be randomized to either AB or BA treatment sequence according to 1:1 ratio.
 
Participants will be randomly assigned to either regimen sequence (AB or BA) in a balanced manner to ensure similar proportions of participants on each sequence, according to a randomization schedule prepared in advance of the study by Statistics, GlaxoSmithKline, using internal validated software (i.e. RandAll).
 

Interim Analysis	
 
No interim analysis is planned.
 

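### The below-quantification rule for the WinNonlin input is not limited to samples after the peak, so an early trace value followed by two or more NQs would delete the real curve

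*SAP*

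**What the plan says.** SAP Section 10.4.2 bases the imputation of concentrations below the quantification limit (NQ) on GUI_51487 and adds: "A brief summary is provided in the table below". One column of that table is headed "Measurable concentrations after more than one consecutive mid-profile NQ", and its footnote reads "a mid-profile NQ is defined as any NQ where measurable concentrations exist both before and after that NQ in the profile".

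The variable that matters for the primary endpoints is described as "PCWNLN: Imputed result for use in WinNonlin analysis". Its row is "PCWNLN 0 NULL NULL NULL NULL". In column order, this means:
- leading NQs become 0;
- a single mid-profile NQ is blanked;
- a run of two or more mid-profile NQs is blanked;
- measurable values after such a run are blanked;
- trailing NQs are blanked.

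For those later measurable values, the summary-statistics variable (PCSTIMP in the table) is also NULL, while the individual-plot variable (PCSTIMSN) is left as it is.

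Section 8.1.2 defines Cmax as "The observed maximum drug concentration" and takes AUC(0-t) as "extrapolated to the last time of quantifiable concentration, calculated as logarithm of trapezoid area". Both are primary endpoints (Section 2.2).

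**The concern.** Blanking stray measurable values after a run of NQs makes sense in the tail of a profile. The table does not say that this is where it applies. A mid-profile NQ is identified only by having a measurable value somewhere before it and somewhere after it.

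A trace value before absorption therefore changes how the NQs that follow it are classed. Without the trace they are leading NQs and become 0. With it they are mid-profile, and if there are two or more in a row, the true absorption and elimination curve is set to NULL. The observed maximum is then discarded, contrary to Section 8.1.2.

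The SAP has no other provision that would catch this:
- It gives no rule for a measurable pre-dose value, although this is a crossover: "Following a washout from Day 6 to Day 11, participants will be crossed over in Period 2".
- Section 4 admits a participant to the bioequivalence population with one evaluable primary parameter in each period, so a trace-level Cmax keeps the participant in.
- The outlier entry in Section 10.4.2 asks for exclusions to be documented but gives no criterion.
- The only sensitivity analysis (Section 8.2) removes participants with inclusion or exclusion violations.

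A correction would have to be decided case by case, in an open-label study, after the profile had been seen.

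**Working it through.** The SAP states no sample size, CV, quantification limit (LLQ) or sampling times, so there is no figure of its own to reproduce. All numerical inputs below are assumptions except the 0.80–1.25 limits and the dosing days.

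**Step 1: apply the PCWNLN row literally to one profile.** Assumed: LLQ 0.1; one-compartment oral curve with lag 1.6 h, absorption rate 0.5/h and half-life 16 h; samples at 0, 0.5, 1, 1.5, 2 h and on to 96 h; linear-up/log-down AUC.

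| Early samples | What reaches WinNonlin | Cmax | AUC(0-t) |
|---|---|---|---|
| No trace, four leading NQs | full curve | 25.1 | 724 |
| Trace 0.12 at 1 h, then one NQ | full curve less that NQ | 25.1 | 725 |
| Trace 0.12 at 0.5 h, then two NQs | 0 and 0.12 only | 0.12 | 0.03 |
| Pre-dose trace 0.12, then three NQs | 0.12 only | 0.12 | 0 |

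The 0.03 is one trapezoid: 0.5 × (0 + 0.12)/2. In the last row AUC(0-t) is zero and its logarithm undefined. In neither of the last two rows is there a terminal phase, so AUC(0-∞) cannot be estimated.

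**Step 2: plausibility of the pre-dose route.** The two doses are 11 days, or 264 h, apart (Day 1 and Day 12). On the assumed curve the 96 h value is 0.59. After a further 168 h it is 0.59 × 2^(−168/16) ≈ 0.0004, far below the assumed LLQ of 0.1. Carry-over above the limit would need much slower elimination or a lower limit. A spurious assay value could still occur.

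**Step 3: effect of one affected profile on the Cmax ratio.** Let n be the participants in one feeding group (fasting and fed are analysed separately), f the trace as a fraction of the true Cmax, the true ratio 1, and the affected period one on treatment A.
- Shift in the log ratio: ln(f)/n.
- Variance of the within-participant log differences: 2·ln(1+CV²) + ln(f)²·(1−2/n)/(n−2), which equals 2·ln(1+CV²) + ln(f)²/n.
- 90% interval: exp[ln(f)/n ± t(0.95, n−2)·√(variance/n)].

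Example with n = 24, CV 25%, f = 0.005:
- The shift is −5.298/24 = −0.221, a ratio of 0.802.
- The variance is 0.121 + 28.07/24 = 1.291.
- The half-width is 1.717·√(1.291/24) = 0.398.
- The interval is 0.538–1.194.

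At CV 25%:

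| n | f = 0.005 | f = 0.02 | f = 0.05 | No affected profile |
|---|---|---|---|---|
| 24 | 0.802 (0.538–1.194) | 0.850 (0.626–1.153) | 0.883 (0.690–1.130) | 1 (0.885–1.130) |
| 36 | 0.863 (0.661–1.128) | 0.897 (0.728–1.105) | 0.920 (0.775–1.092) | 1 (0.907–1.103) |
| 48 | 0.895 (0.731–1.098) | 0.922 (0.785–1.082) | 0.939 (0.821–1.075) | 1 (0.919–1.088) |
| 60 | 0.915 (0.776–1.080) | 0.937 (0.821–1.069) | 0.951 (0.850–1.064) | 1 (0.928–1.078) |

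For n = 24 and 36 with CV 20%, 25% and 30%, the lower limit is below 0.80 in all 18 combinations. The mildest is 0.783 (n = 36, CV 20%, f = 0.05). At n = 48 and f = 0.05, and at n = 60 and f = 0.02 or 0.05, the interval passes. An affected period on treatment B gives the reciprocal results and threatens the upper limit instead.

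**Step 4: simulation.** With a trace of 0.12 against a Cmax of 25.1 (f ≈ 0.005), CV 25% and 4,000 trials per size, the chance of meeting 0.80–1.25 for Cmax fell from 85% to 0% at n = 24, from 96% to 0% at n = 36 and from 99% to 3% at n = 48.

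**The case against.** The strongest reply is that the table is only a summary. Sections 10.2.3 and 10.4.2 both defer to GUI_51487, and a post-peak limit or a pre-dose rule is just the kind of detail a summary drops. This stands as a reason to consult the guide first. It does not settle the matter, because the table as printed is the only rule a reader of the SAP can apply, and nothing in the SAP restricts it.

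Several stronger readings are tempting, but the document does not support them:
- *A single trace value is enough to destroy a profile.* It is not. At least two consecutive NQs must follow; with one, the profile survives.
- *A false but plausible AUC always enters the analysis.* After a pre-dose trace, AUC(0-t) is zero and drops out on the log scale, and AUC(0-∞) is missing in every affected profile. The false value is mainly Cmax.
- *The fed group is at greater risk through delayed absorption.* The SAP contains nothing on lag or absorption under either condition.
- *One such profile always sinks the study.* That depends on n and on the size of the trace.
- *The difference between plotted and analysed curves is itself an error.* The SAP deliberately keeps separate variables for separate uses. An intact individual plot beside a trace-level Cmax would help the team notice the problem, although no correction is prescribed.

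**Conclusion.** The concern holds in a limited form. As printed, the rule reaches samples before the peak, feeds the primary parameters, and can conflict with the SAP's own definition of Cmax. It needs a specific pattern: a pre-dose or early trace, then two or more NQs, then measurable absorption. That pattern is probably rare, and its frequency cannot be estimated from the SAP.

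If it occurs once, Cmax fails the 0.80–1.25 criterion in every case computed at 24 or 36 participants per feeding group. At 48 or 60 the result depends on how small the trace is. These figures assume a true ratio of 1, a within-subject CV of 20–30% for the 24 and 36 cases (25% for the larger sizes tabulated), and a trace of 0.5–5% of the true Cmax.

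This is a minor to moderate point. It deserves correction because the change is small and a single occurrence could decide a primary endpoint.

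**What to change.** First compare the table with GUI_51487. Then add below it:

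> *Blanking of measurable concentrations that follow two or more consecutive mid-profile NQs applies only to samples after the observed maximum of that period. Two or more consecutive NQs that follow only a pre-dose or isolated trace value and precede the absorption phase are treated as leading NQs (0), and later measurable concentrations are kept.*

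Apply this to PCWNLN and PCSTIMP alike, and state separately how a measurable pre-dose value is itself handled.

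Leave the single-NQ column unchanged. A broader rule setting every pre-peak NQ to 0 would turn one spurious NQ between two rising measurable values from NULL into 0 and bias the AUC downward.

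While editing, correct Section 10.3.4, which sends the reader to Section 10.4.1 for the quantification-limit rules; they are in 10.4.2.

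The cost is a short SAP addition and a small change to the PKCNC derivation, to be made before database freeze. If the guide contains no such limit, a documented study-specific exception is also needed.
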